#### **4.2.6 Safety analysis**

Safety summaries will be descriptive only. No formal statistical analyses are planned for safety data. All data will be reported using the safety population unless specified otherwise.

The following sections describe the planned safety summaries for safety variables as defined in section 3.6. However, additional safety summaries (not specified in this SAP) may need to be produced to aid interpretation of the safety data.

##### **4.2.6.1 Adverse Events**

Summary tables will include TEAEs as defined in section 3.6.1, unless otherwise specified.

An AE overview summary table will be produced showing the number (%) of participants with at least one AE in each of the following categories:

- Any AE
- Any AE with an outcome of death
- Any SAE

- Any AE leading to discontinuation of study treatment
- Any severe AE
- Any AESI
- Any AE leading to withdrawal from study

For all categories above, the number (%) of participants with at least one causally related AE in that category will also be provided.

An additional table will be produced showing the incidence of participants with the following type of adjudicated events:

- RPOA (type 1 and 2)
- SIF
- Primary osteonecrosis,
- Pathological fracture

The number of participants treated per treatment group will be used as the denominator to calculate percentages.

Summary tables will be produced by MedDRA SOC and PT for the following categories:

- AEs
  - By age group as defined in section 4.2.8
  - By sex
  - By periods as defined in section 3.1.6.
  - By ADA categories as defined in section 3.4.2
- Severe AEs
- By periods as defined in section 3.1.6. Causally related AEs and SAEs
  - By periods as defined in section 3.1.6.
- SAEs with outcome death
- SAEs
  - By periods as defined in section 3.1.6.
  - By ADA categories as defined in section 3.4.2
- AEs leading to discontinuation of study treatment
- AESIs
  - By periods as defined in section 3.1.6
  - Separate table to be provided for each AESI category as defined in section 3.6.1.1
    - By periods as defined in section 3.1.6
    - Joint related AESI table by study periods will also include the exposure adjusted rates, where AE event rate (per 100 participant years) is defined as the number of

participants with that AE divided by the total number of days at risk for AEs across all participants in given treatment arm and multiplied by  $365.25 \times 100$  to present in terms of per 100 participant years.

- Most common non-serious AEs defined as AEs occurring in at least 5% of participants overall (in total column). For each SOC/PT, the number (%) of participants reporting at least one event at each level of summarisation will be presented. Participants with multiple occurrences of the same AE, the event will only be counted once per SOC/PT. Those will be sorted by international order for system organ class and in alphabetical order for preferred term.

In addition, a table with AEs and event counts sorted by decreasing frequency on preferred term will be produced as well as AEs by maximum intensity on preferred term by SOC and PT.

Additional table presenting mapping of AESIs will be produced.

A separate table with key participant information will be produced for:

- SAEs with outcome of death
- SAEs
- AEs leading to discontinuation of study treatment

A separate listing will be produced for the following AE categories:

- AEs
- SAEs
- AESIs
- AEs leading to discontinuation of study treatment

For any AE with change in intensity, listings will report all intensities as well as associated actions.

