### Treatments and treatment duration:

The study consists of a screening period of up to 45 days (one or more visits), a 12-week double-blind treatment period (10 scheduled visits), and a 24-week follow-up period (3 scheduled visits and 4 phone calls).

After screening and confirmation of eligibility criteria, eligible participants will be randomised on Day 1 at a 1:1:1:1:1 ratio to receive MEDI7352 doses or placebo. Participants will receive a total of 6 CCI injections (every 2 weeks [Q2W] at Day 1, weeks 2, 4, 6, 8 and 10):

- Cohort 1: MEDI7352 CCI
- Cohort 2: MEDI7352 CCI
- Cohort 3: MEDI7352 CCI
- Cohort 4: MEDI7352 CCI
- Cohort 5: Placebo

Participants who complete the treatment period will come in for their end-of-treatment (EOT) visit at Week 12 and then enter the follow-up period. Participants who permanently discontinue investigational product (IP) will be asked to complete study assessments at the early termination (ET) visit (Week 12 assessments) as soon as possible and then enter the follow-up period. All participants are expected to complete the EOT/ET visit and the 24-week follow-up period.

The study incorporates two interim analyses, detailed in section 5.

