#### **3.1.6.2 On treatment**

On treatment is defined from the day and time of first IP administration throughout to the last IP administration +14 days, based on MEDI7352 half-life of 3-4 days. Participants that are randomised and do not receive IP will not be part of 'on treatment' period.

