### 3.1.6.3 Post treatment

Post treatment is defined from last IP+15 days through to the date of last study assessment.

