## 6 CHANGES OF ANALYSIS FROM PROTOCOL

- The final analysis and its reporting will be split to two deliverables that would be supported by two database locks at timepoints specified in section 1. This is to evaluate the efficacy data once all participants complete the treatment period as it is not anticipated that this data will change rather than waiting once all participants complete the study especially after the follow-up period was extended from 12 to 24 weeks.
- Single imputation will be performed only for the primary and key secondary endpoints as it is not meaningful to perform the single imputation for endpoints that will only be summarised.
- The sequentially rejective multiple comparison approach includes not just pairwise comparisons, but also the dose response curve for the WOMAC pain subscale score. In addition, MCP-MOD analyses of the remaining key secondary endpoints will not be performed.
- Additional supplementary analyses not specified in the protocol were added for comparative purposes within the industry. Those are: ANCOVA analysis of the primary endpoint and WOMAC pain subscale score key secondary endpoint using singly imputed LOCF cases as well as ANCOVA analysis of the WOMAC pain subscale score key secondary endpoint using multiply imputed cases that were imputed using the sampling from normal distribution approach.
- The protocol presents the concomitant medication and therapies as a safety endpoint. However, this data does not necessarily evaluate the safety and hence was moved as part of participant disposition which is in alignment with AZ standard shells reporting.
- CCI [REDACTED].
- The definition of the treatment emergent AEs was clarified to account for instances where a participant withdraws from the study over a phone call and disposition (DS) page in eCRF is populated without the corresponding visit being recorded. In addition, the change in relationship was removed as pre-treatment AE that changes the relationship would need to be entered in the database as a new AE with a start date on or after the first IP administration date and hence would automatically become a treatment emergent AE as per the first part of the definition.
- Other secondary endpoints, DSIS and rescue medication use will be summarised and analysed using available data on protocol specified visits and not just those visits specified in the definition of the endpoint itself (Week 2, 4, 6, 8, 10, 12 and 18).

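### By-period adverse event tables give crude percentages for windows of about 85 and 167 days, so on-drug and off-drug incidence cannot be compared

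*SAP*

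**What the plan says.** Two definitions in the SAP fix the periods. Section 3.1.6.2: "On treatment is defined from the day and time of first IP administration throughout to the last IP administration +14 days". Section 3.1.6.3: "Post treatment is defined from last IP+15 days through to the date of last study assessment". Under Treatments and treatment duration in section 1.2, injections are given "every 2 weeks [Q2W] at Day 1, weeks 2, 4, 6, 8 and 10", and the study has "a 12-week double-blind treatment period (10 scheduled visits), and a 24-week follow-up period (3 scheduled visits and 4 phone calls".

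Section 4.2.6.1 then asks for SOC/PT tables split by these periods for AEs, causally related AEs and SAEs, SAEs, AESIs and each AESI category. Severe AEs appear to be included too, although the bullet layout is broken there.

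On the denominator, section 4.2.6.1 says: "The number of participants treated per treatment group will be used as the denominator to calculate percentages". That sentence follows the adjudicated joint-event table, so its reach is uncertain. If it covers only that table, the default in section 4.1 applies, which is the analysis-set total for the cohort. For safety tables both readings give everyone treated, whichever period is shown.

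One table goes further: "Joint related AESI table by study periods will also include the exposure adjusted rates". Its rate is the number of participants with the event divided by the arm's summed days at risk, scaled to 100 participant-years.

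**The concern.** A by-period AE table exists to show whether events cluster while participants are on drug or after they have stopped. A crude percentage can do that only if the periods are about equally long, and here the post-treatment window is about twice the on-treatment one. A flat hazard would read as an excess after treatment, and a real on-drug excess of up to about twofold could look flat or reversed.

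The SAP recognises the need for a time-at-risk rate but supplies it only for joint-related AESIs. The other by-period tables, including those for the serious or severe infection and hypersensitivity AESI categories, have none.

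The planned joint rate is itself loosely defined. It is described by study periods, which is the section 3.1.5 term, under a bullet that uses the section 3.1.6 periods. Its days at risk are not said to be those of the period shown.

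**Working it through.** The SAP gives no day counts or event rates on this point, so there is no stated figure to reproduce.

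**Period lengths for a participant who receives all six doses**
- Last dose at Week 10: 10 × 7 + 1 = Day 71, using the day-numbering rule of section 3.1.7.
- On treatment: 71 + 14 = 85 days.
- End of study: 12 + 24 = 36 weeks, or 252 days.
- Post treatment: 252 − 85 = 167 days.
- Numbering the end of study as Day 253 gives 168 days. Nominal labels (Day 70) give 84 and 168. The ratio of post-treatment to on-treatment time is 1.96 to 2.00.

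**Between periods.** Assume a constant hazard, equal in both periods. Crude incidence over T days at r events per participant-year is 1 − exp(−r × T / 365.25).

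| Assumed rate per 100 participant-years | On treatment, 85 days | Post treatment, 167 days | Ratio |
|---|---|---|---|
| 5 | 1.16% | 2.26% | 1.95 |
| 50 | 10.98% | 20.44% | 1.86 |
| 200 | 37.2% | 59.9% | 1.61 |

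**Between arms, on treatment.** A participant who receives 1, 2, 3, 4, 5 or 6 doses has 15, 29, 43, 57, 71 or 85 on-treatment days. At 50 per 100 participant-years, incidence over 43 days is 1 − exp(−0.5 × 43 / 365.25) = 5.72%. Suppose a share of each arm stops after three doses:
- 10% stopping: 0.9 × 10.98% + 0.1 × 5.72% = 10.46%.
- 20% stopping: 0.8 × 10.98% + 0.2 × 5.72% = 9.93%.

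The ratio is 0.95. A more extreme case, 10% versus 30% stopping after one dose, gives 10.09% versus 8.30% (ratio 0.82).

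**The planned joint-AESI rate.** Its scaling is correct: one participant with an event in 36,525 days gives 1 / 36,525 × 365.25 × 100 = 1 per 100 participant-years. If the denominator were whole-study days rather than period days, and events are uncommon, the on-treatment rate would be 85 / 252 = 34% of the truth and the post-treatment rate 167 / 252 = 66%.

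**Effect of the definition of days at risk.** With days counted within the period and stopped at first event, a true 50 per 100 participant-years returns 50.0 in both periods. With full period days, it returns 47.2 on treatment and 44.7 post treatment; a true 200 returns 160 and 131. The stopping rule therefore has to be written down.

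**The case against.** The main comparison in a randomised trial is between arms within a period, and the planned windows are the same in every arm. Whole-study TEAE tables are also produced; exposure, doses received and discontinuation reasons are reported by arm; and section 4.2.6 makes safety descriptive and allows further summaries. All of that stands. It limits the point to how the period tables are read, but it does not commit the SAP to any rate that would make the two periods comparable.

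A reader might infer several stronger things that the SAP does not support:

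- **That arms with more early stopping necessarily look safer.** The stopping shares above are assumptions. A participant who stops because of an AE has already been counted on treatment, so the direction is not assured, and arms with equal stopping are not distorted.
- **That early stoppers gain post-treatment time.** Section 1.2 sends them to the ET visit as soon as possible and then into the same 24-week follow-up. Someone stopping after dose 2, with ET near Day 29, would be followed to about Day 197, about 168 post-treatment days and much like a completer.
- **That some participants have a post-treatment window of only about 83 days.** Section 6 does say "especially after the follow-up period was extended from 12 to 24 weeks", but section 3.1.8 places assessments under earlier protocol versions at Week 28, which is 16 weeks after Week 12. The earlier length is therefore not secure from this document, and no counts are given.
- **That sparser contact in follow-up biases the comparison.** There are "a 24-week follow-up period (3 scheduled visits and 4 phone calls", against 10 visits in 12 weeks. But the question in section 3.6.1.2 covers the whole interval since the last contact, so fewer contacts do not shorten the reporting window.

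**Conclusion.** The point holds for the comparison between periods. For completers under the 24-week follow-up, the post-treatment window is about twice the on-treatment one, and at an equal hazard the crude percentages differ by a factor of about 1.6 to 1.95 over 5 to 200 events per 100 participant-years. The period lengths come from the SAP; the constant, equal hazard and the event rates are assumptions.

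The between-arm effect is secondary. It needs unequal early stopping, acts mainly on treatment, and is about 5% relative for a 10-point gap in stopping after three doses.

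The joint-related AESI table is the only one with a rate, and that rate is secure only once its days at risk are tied to the period. This is a weakness of presentation and interpretation: no test, estimand or decision rule is affected. It is still worth correcting, because these tables are planned specifically to separate on-drug from off-drug events.

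**What to change.** Amend section 4.2.6.1 in three respects:

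1. Add participant-year rates beside the percentages in every AE table split by the section 3.1.6 periods.
2. Define days at risk, for the joint-related AESI table as well, as each participant's days within that period up to the first such event or the end of the period. Refer to section 3.1.6 by number in place of the looser study-period wording.
3. Use participants who entered the period as the denominator for that period's percentages.

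The planned joint-AESI formula cannot simply be copied, since it is neither tied to the period nor stopped at first event. The cost is SAP wording, a modest extension of a derivation already planned, and extra columns in the period tables. Safety stays descriptive and no formal analysis changes.

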#### **4.2.6.2 Joint replacement surgeries**

Incidence of participants with the joint replacement surgeries occurred during the study participation will be summarised by treatment group depending on whether the surgeries were elective or due to an AE.

#### **4.2.6.3 Pregnancies**

Pregnancies entered on the pregnancy report (PREGREP) page in eCRF will be reconciled against safety database and the reconciled entries on (PREGREP) page in eCRF will be listed.

#### 4.2.6.4 Laboratory results

Tables with descriptive summaries (mean, SD, median, minimum, and maximum) of actual (absolute) values and changes from baseline values will be produced for each treatment group at each visit. Tables will be produced for tests specified in section 3.6.8 except for urine drug screen, urine pregnancy test, serology, and endocrinology. Participants with abnormal results of these tests except for urine pregnancy test will be only listed including all available results.

Central laboratory reference ranges will be used for the identification of abnormalities. Shift tables will be produced for the same parameters for which summary tables will be produced with the exception of urinalysis to display low, normal, and high values.

The shift tables will present baseline and maximum/minimum on-treatment value, as applicable for each parameter and will include participants with both baseline and post-baseline data. The exception would be Haemoglobin A1c that is evaluated only at baseline and Week 32 hence this shift table will present baseline and maximum/minimum value during the study.

For urinalysis parameters collected as for example: Negative, Small, Moderate or Large, shift tables from baseline to maximum value during treatment will be provided. This will apply to bilirubin, blood, leucocytes, glucose, protein and ketones. Key participant information table listing only participants and assessments with abnormal values will be produced.

Laboratory values will also be presented as box plots, for absolute values and changes from baseline. All protocol defined visits will be summarised.

Each plot will show the following details:

- Mean (symbol within each box)
- Median (horizontal line within each box)
- Q1 and Q3 (bottom and top of each box)
- Whiskers extending to the most extreme observation within 1.5 times the interquartile range from the nearest quartile.
- Outliers outside the whiskers displayed individually.
- Reference ranges shown as dotted lines on the analysis value plots, not relevant to the change from baseline plot. If more than one reference range is available for an assessment (example: due to gender differences) then the narrowest range will be used in the graph.

The plots will be prepared for each test within the laboratory categories:

- Haematology: hemoglobin, hematocrit, RBC count, platelet count (or estimate), WBC count, WBC differential

- Serum chemistry: albumin, total and direct bilirubin, total protein, calcium, ALP, ALT, AST, GGT, BUN, creatinine, glucose, sodium, potassium, chloride, bicarbonate, phosphorus, LDH, uric acid, CRP, cholesterol, triglycerides, creatine phosphokinase.
- Coagulation panel: prothrombin time, activated partial thromboplastin time, fibrinogen
- Urinalysis: pH, specific gravity.

In addition, listings of abnormal safety laboratory results will be prepared. The listings will include only participants and tests with at least one abnormal value reported. All available results for that specific test will be presented in order to see the change over time.

#### 4.2.6.4.1 Liver enzyme elevations and Hy's law

Liver function laboratory tests assessments (scheduled and unscheduled) up to 30 days after the last dose of study treatment will be considered.

The following summaries will include the number (%) of participants with at least one post-baseline liver function assessment who have:

- Elevated ALT, AST and total bilirubin as
  - ALT  $\geq 3\times$  to  $<5\times$ ,  $\geq 5\times$  to  $<10\times$ ,  $\geq 10\times$  to  $<20\times$ ,  $\geq 20\times$  upper limit of normal (ULN)
  - AST  $\geq 3\times$  to  $<5\times$ ,  $\geq 5\times$  to  $<10\times$ ,  $\geq 10\times$  to  $<20\times$ ,  $\geq 20\times$  ULN
  - Total bilirubin  $\geq 2\times$  ULN
  - ALT or AST  $\geq 3\times$  to  $<5\times$ ,  $\geq 5\times$  to  $<10\times$ ,  $\geq 10\times$  to  $<20\times$ ,  $\geq 20\times$  ULN
  - ALT or AST  $\geq 3\times$  ULN and total bilirubin  $\geq 2\times$  ULN (Potential Hy's law): The onset date of ALT or AST elevation should be prior to or on the date of total bilirubin elevation.

Percentages will be based on the number of participants who have at least one measurement available.

To identify potential Hy's Law cases, a listing of participants who have ALT or AST  $\geq 3\times$  ULN and total bilirubin  $\geq 2\times$  ULN (not necessarily at the same time) following first dose of study treatment will be provided.

A shift table will also present maximum ALT and AST observed values by maximum total bilirubin observed value, expressed as multiples of ULN. Categories will be included for:

- ALT  $<3$ ,  $\geq 3\times$  to  $<5\times$ ,  $\geq 5\times$  to  $<10\times$ ,  $\geq 10\times$  to  $<20\times$ ,  $\geq 20\times$  ULN
- AST  $<3\times$ ,  $\geq 3\times$  to  $<5\times$ ,  $\geq 5\times$  to  $<10\times$ ,  $\geq 10\times$  to  $<20\times$ ,  $\geq 20\times$  ULN
- Total bilirubin  $<2\times$ ,  $\geq 2\times$  ULN

Key participant information table of participants with potential Hy's law will be produced.

#### 4.2.6.5 Vital signs results

Table with descriptive summaries (n, mean, SD, median, minimum, maximum, Q1 and Q3) of observed values and changes from baseline values for each treatment group at each protocol scheduled time point will be produced for the following vital signs tests:

- Systolic BP
- Diastolic BP
- Pulse rate
- Respiratory rate
- Temperature

In addition, shift table from baseline to minimum/maximum value during treatment will be produced for all above mentioned parameters. The reference ranges provided in section 3.6.5 will be used to determine whether the minimum/maximum value during treatment is within the normal range or not.

A by-visit incidence summary of orthostatic hypotension will be prepared for the following result categories:

- Criteria met
- Confirmed
- Symptomatic

A table presenting the changes in postural BP at each timepoint/ visit will be produced. Consequently, the supine readings from VS (for non-dosing visits) and VS1 (for dosing visits) eCRF forms as well as postural readings from VS2 eCRF form will be summarised descriptively by cohorts at each visit and all available timepoints as per all three eCRF forms. In addition, a listing of confirmed and symptomatic orthostatic hypotension cases will be prepared. The listing will include all participants with at least one assessment indicated as a confirmed or symptomatic case of orthostatic hypotension. All available results will be presented in order to see the change over time.

Vital signs data for participants/parameter with at least one abnormal result for the below mentioned parameters will be listed:

- Systolic BP (Including assessments from VS2 page in the eCRF)
- Diastolic BP (Including assessments from VS2 page in the eCRF)
- Pulse rate
- Respiratory rate
- Temperature

#### **4.2.6.6 ECG results**

Overall evaluation of electrocardiogram (ECG) will be summarised at each timepoint/visit reporting the number (%) of participants presenting a normal, abnormal not clinically significant or abnormal clinically significant evaluation.

In addition, a listing of abnormal ECG results will be prepared. The listing will include all participants with at least one abnormal value reported. All available results will be presented in order to see the change over time.

#### **4.2.6.7 Physical examination findings**

Findings, that is data of participants/examinations with at least one abnormal result will be listed for all available visits including unscheduled visits for all participants.

